14.2.1 Amendments to the Protocol

Amendments to the protocol shall be planned, documented and signature authorized prior to implementation. If an amendment to the protocol is required, the amendment will be originated and documented by the Coordinating Center in collaboration with Sponsor. The written amendment must be reviewed and approved by the Sponsor, and submitted to the IRB at the Study Chairs' facility for the board's approval.

Amendments specifically involving change to trial design, risk to patient, increase to dosing or exposure, subject number increase, addition or removal of new tests or procedures, shall be reviewed and approved by the IRB at the Study Chairs' facility. Once approved, the amendment will be distributed to the participating sites for submission to their institutional review boards (IRB) or Ethics Committees (EC). Updates to the participating site ICF must be reviewed and approved by the Coordinating Center prior to the site submission to their IRB.

The amendment will be submitted formally to the FDA or other regulatory authorities [REDACTED] [REDACTED] applicable, after IRB approval and specifically when an increase to dosing or patient exposure and/or subject number has been proposed; or, when the addition or removal of an Investigator is necessitated.

Items requiring a protocol amendment with IRB and/or FDA approval include, but are not limited to, the following:

- Change to trial design
- Risk to patient
- Increase to dose or patient exposure to drug
- Subject number increase
- Addition or removal of tests and / or procedures
- Addition/removal of a new Investigator

It should be further noted that, if an amendment to the protocol substantially alters the trial design or the potential risks to the patients, their consent to continue participation in the trial should be obtained.

14.2.2 Documentation Required to Initiate a Trial

Before the trial may begin, certain documentation required by FDA regulations must be provided by the Investigator to the [REDACTED].

Documents at a minimum required to begin a trial in the US include, but are not limited to, the following:

- A copy of the Form FDA 1572 signed and dated by the Principal Investigator from the participating site.
- A copy of a current CV and Medical Licenses for all Investigators listed on the Form FDA 1572.
- Lab credentials (i.e. CAP, CLIA, ranges, etc.) as applicable for all labs listed on the Form FDA 1572 being used by the participating site.
- A copy of the Protocol Acceptance Page signed and dated by the Principal Investigator from the participating site.
- A copy of the Financial Disclosure completed and signed by all investigators listed on the Form FDA 1572 for the participating site.
- A copy of the delegation of authority log must be sent to the Coordinating Center
- A copy of documentation of training for study staff members must be sent to the Coordinating Center.
- A copy of the consent form that has been approved by the Coordinating Center and the Institutional Review Board for the participating site.
- The IRB approval letter for the participating site.
- The IRB Committee Roster for the participating site.
- The drug destruction policy for the participating site.
- A copy of a fully executed contract must be on record in the contracts office
- Site qualification reports, where applicable;

- Verification of Principal Investigator acceptability from local and/or national debarment list(s)

14.2.3 Trial Documentation and Storage

The site PI must maintain a list of appropriately qualified persons to whom he/she has delegated trial duties and should ensure that all persons assisting in the conduct of the trial are informed of their obligations. All persons authorized to make entries and/or corrections on the CRFs are to be included on this document. All entries in the patient's CRF are to be supported by source documentation where appropriate.

Source documents are the original documents, data, records and certified copies of original records of clinical findings, observations and activities from which the patient's CRF data are obtained. These can include, but are not limited to, hospital records, clinical and office charts, clinical research unit charts, laboratory, medico-technical department and pharmacy records, diaries, microfiches, ECG traces, copies or transcriptions certified after verification as being accurate and complete, photographic negatives, microfilm or magnetic media, X-rays, and correspondence.

The PI and trial staff for each clinical trial site are responsible for maintaining a comprehensive and centralized filing system (Site Trial File/SSF or ISF) of all trial-related (essential) documentation, suitable for inspection at any time by representatives from the Sponsor and/or applicable regulatory authorities. The ISF/SSF must consist of those documents that individually or collectively permit evaluation of the conduct of the trial and the quality of the data produced. The ISF/SSF should contain as a minimum all relevant documents and correspondence as outlined in ICH GCP Section 8 and 21 CFR Part 312.57, including key documents such as the IB and any amendments, protocol and any amendments, signed ICFs, copies of completed CRFs, IRB approval documents, Financial Disclosure forms, patient identification lists, enrollment logs, delegation of authority log, staff qualification documents, laboratory normal ranges, records relating to the trial drug including accountability records. Drug accountability records should, at a minimum, contain information regarding receipt, shipment, and disposition. Each form of drug accountability record, at a minimum, should contain PI name, date drug shipped/received, date, quantity and batch/code, or lot number for identity of each shipment. In addition, all original source documents supporting entries in the CRF must be maintained and be readily available.

The Sponsor shall maintain adequate investigational product records and financial interest records as per 21CFR Part 54.6 and Part 312.57 for no less than 2 years after the last marketing application has been approved by FDA; or, in the event that the marketing application has not been approved by FDA, for no less than 2 years after the last shipment / delivery of the drug for investigational use is discontinued and FDA has been notified of the discontinuation.

The IRB shall maintain adequate documentation / records of IRB activities as per 21CFR Part 56.115 for at least 3 years after completion of the research.

The Site Investigator shall maintain adequate records of drug disposition, case histories and any other trial-related records as per 21 CFR Part 312.62 for no less than 2 years after the last marketing application has been approved by FDA; or, in the event that the marketing application has not been approved by FDA, for no less than 2 years after the last shipment / delivery of the drug for investigational use is discontinued and FDA has been notified of the discontinuation.

To enable evaluations and/or audits from regulatory authorities or from the Sponsor or its representative, the investigator additionally agrees to keep records, including the identity of all participating patients (sufficient information to link records e.g., CRFs and medical records), all original, signed informed consent forms, and copies of all CRFs, SAE Reporting forms, source documents, detailed records of treatment disposition, and related essential regulatory documents. The documents listed above must be retained by the investigator for as long as needed to comply with national and international regulations (generally 2 years after discontinuing clinical development or after the last marketing approval). The VICC Multi- Institutional Coordinating Office will notify the investigator(s)/institutions(s) when the trial- related records are no longer required.

If the investigator relocates, retires, or for any reason withdraws from the trial, both Coordinating Center and the Sponsor should be prospectively notified. The trial records must be transferred to an acceptable designee, such as another investigator, another institution, or to sponsor. The investigator must obtain the sponsor written permission before disposing of any records, even if retention requirements have been met. All trial files will be maintained by the Coordinating Center throughout the trial, and prepared for long term storage by Coordinating Center at the conclusion of the trial.

14.2.4 Data Collection

Data will be collected and entered by the participating sites using a centralized Electronic Data Capture (EDC) system called REDCap.

The Vanderbilt University Office of Research will be used as a central location for data processing and management. Vanderbilt University, with collaboration from a consortium of institutional partners, has developed a software toolset and workflow methodology for electronic collection and management of research and clinical trial data. REDCap (Research Electronic Data Capture) is a secure, web-based application that is flexible enough to be used for a variety of types of research. REDCap provides an intuitive user interface that streamlines project development and improves data entry through real-time validation rules (with automated data type and range checks). REDCap also provides easy data manipulation (with audit trails for reporting, monitoring and querying patient records) and an automated export mechanism to common statistical packages (SPSS, SAS, Stata, R/S-Plus). In addition to traditional data capture functionality, REDCap's survey capabilities are a powerful tool for building and managing online surveys. The research team can create and design surveys in a web browser and engage potential respondents using a variety of notification methods. All data collection projects rely on a thorough, study-specific data dictionary, defined by all members of the research team in an iterative, self-documenting process. This iterative development and testing process results in a well-planned and individualized data collection strategy.

REDCap servers are housed in a local data center at Vanderbilt, and all web-based information transmission is encrypted. REDCap was developed specifically around HIPAA-Security guidelines and is recommended to Vanderbilt researchers by both our Privacy Office and Institutional Review Board. REDCap has been disseminated for local use at more than 940 other academic/non-profit consortium partners in 75 countries. Vanderbilt leads the REDCap Consortium, which currently supports more than 99,000 projects and 128,000 users. More information about the consortium and system security can be found at [REDACTED]

In order to maintain confidentiality, only trial number, patient number, initials and year of birth will identify the patient in the CRF. If the patient's name appears on any other document (e.g. laboratory report), it must be obliterated on the copy of the document to be supplied to [REDACTED] and replaced instead with the patient number and patient's initials. The investigator will maintain a personal patient identification list (patient numbers with corresponding patient identifiers) to enable records to be identified and verified as authentic. Patient data/information will be kept confidential, and will be managed according to applicable local, state, and federal regulations.

All data requested on the CRF must be supported by and be consistent with the patient's source documentation. All missing data must be explained. When a required laboratory test, assessment, or evaluation has not been done or an "Unknown" box is not an option on the CRF, a note should be created verifying that the field was "Not Done" or "Unknown". For any entry errors made, the error(s) must be corrected, and a note explaining the reason for change should be provided.

15.0 SAFETY MONITORING AND REPORTING ADVERSE EVENTS

15.1 The Data and Safety Monitoring Board (DSMB) will oversee the conduct of the study. The DSMB will receive confidential reports every 6 months. The focus of these reports will be on study progress and safety. The DSMB will be

responsible for decisions regarding possible termination and/or early reporting of the study and they will have access to any available data needed to inform their decisions. The Data and Safety Monitoring Committee (DSMC) of the Vanderbilt Ingram Cancer Center (VICC) will also oversee the study safety.

15.2 The Data and Safety Monitoring Committee (DSMC)

The Vanderbilt-Ingram Cancer Center (VICC) oversees patient safety and data monitoring for its investigator-initiated and NIH-NCI funded clinical trials through its Data and Safety Monitoring Committee (DSMC). The purpose of the DSMC is to ensure the efficient implementation and management of VICC Data and Safety Monitoring Plan (DSMP). The Committee maintains authority to intervene in the conduct of studies as necessary to ensure clinical research performed at VICC achieves the highest quality standards.

The VICC DSMC meets on a quarterly basis and ad hoc to discuss data and safety monitoring of clinical trials and to oversee the VICC DSMP. Internal audits for compliance with adverse event reporting, regulatory and study requirements, and data accuracy and completion are conducted according to the VICC DSMP according to study phase and risk. The committee reviews all serious adverse events (SAE) on Vanderbilt sponsored investigator-initiated studies on a quarterly basis and provides DSMC SAE review reports to the Vanderbilt IRB.

15.3 VICC Multi-Institutional Coordinating Center

The trial additionally will be monitored by the VICC Multi-Institutional Coordinating Center. The actual frequency of monitoring will depend on the enrollment rate and performance of the site. Monitoring will be conducted through onsite and remote monitoring, teleconferences with the Investigator and site staff, and appropriate communications by mail, fax, email, or telephone. The purpose of monitoring is to ensure that the study is conducted in compliance with the protocol, standard operating procedures (SOPs), and other written instructions, and to ensure the quality and integrity of the data.

During scheduled monitoring visits, investigators and the investigational site staff must be available to discuss the progress of the trial, make necessary corrections to case report form entries, respond to data clarification requests, provide required regulatory documents, and respond to any other trial-related inquiries of the monitor. In addition to the above, the Sponsor, CPP, and the FDA may review the conduct or results of the study at the investigational site.

15.3 Adverse Event Reporting Purpose.

Adverse event data collection and reporting, which are required as part of every clinical trial, are done to ensure the safety of patients enrolled in the studies as well as those who will enroll in future studies using similar agents. Adverse events are reported in a routine manner at scheduled times during a trial. Certain adverse events must be reported in an expedited manner. Adverse events should be reported from the start of study drug through 30 days after the last dose of study treatment.

Any event that occurs more than 30 days after the last dose of study agent and is attributed (possible, probable, or definite) to the study agent(s) must be reported according to the instructions outlined in section 15.

15.4 Adverse Event Definitions.

15.4.1 Adverse Event (AE)

An adverse event is any undesirable sign, symptom or medical condition or experience that develops or worsens in severity after starting the first dose of study treatment or any procedure specified in the protocol, even if the event is not considered to be related to the study.

Abnormal laboratory values or diagnostic test results constitute adverse events only if they induce clinical signs or symptoms or require treatment or further diagnostic tests.

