3.1 Eflornithine (NSC-337250) (103678.)

a. DESCRIPTION

This trial will use low dose oral eflornithine hydrochloride. Eflornithine is a member of the following drug classes: 1) inhibitor of ornithine decarboxylase (ODC), 2) hair growth retardant. Eflornithine is FDA approved as a cream for female hirsutism, and in intravenous form for trypanosomiasis. The oral tablet form is not available outside of the clinical trial setting in the U.S. The formulation used in this trial is similar to that reported previously in a Phase III colon adenoma clinical trial in combination with sulindac.[28] This formulation of eflornithine is under study in U.S. and international trials both for chemoprevention (low dose) and cancer therapy (high dose). (See Appendix).

b. TOXICOLOGY

Contraindications: Prior hypersensitivity to eflornithine. Precaution in patients with bone marrow suppression or hematologic disorders.

Side effects: The side effects reported herein are those observed in all studies to date, and for both high and low dosing. This study will utilize the low dose of eflornithine (500mg per day).

Common Side Effects (most frequently reported AEs in NCI, DCP-sponsored chemoprevention studies): diarrhea (9.0%), headache (7.5%), nausea (6.5%), hearing loss (5.6%), tinnitus (4.3%) and asthenia (4.7%).

Less Common Side Effects (2 – 3%): epigastric pain, flatulence, dyspepsia, anemia, dizziness and skin rash.
Rare Side Effects (1 - 2%): stomatitis, rhinitis, insomnia, infections, vomiting, vasodilation, dry mouth, constipation, dry skin, menstrual disorders, pharyngitis, emotional lability, pruritis, myalgia, and pain (miscellaneous).

There have been rare but serious reports of seizures in some subjects receiving high doses of eflornithine (15 g/day, ~215 mg/kg-bw/day). These instances occurred in subjects who were trypanosomiasis, glioma, or AIDS patients, and were suspected of having an impaired blood-brain barrier due to their disease or prior drug treatments.

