9.0 TOXICITIES TO BE MONITORED AND DOSAGE MODIFICATIONS

9.1 This study will utilize the CTCAE version 4.0 (NCI Common Terminology Criteria for Adverse Events) for toxicity and Serious Adverse Event (SAE) reporting.

9.2 Guidelines for monitoring expected and unexpected symptoms/toxicities are defined below.

All interventions can be dose reduced based on toxicity or participant perceived toxicity. All toxicities are recorded on the Adverse Events Summary Form. All patients who discontinue treatment after randomization will continue to be followed for endoscopy results.

Guidelines for Monitoring of Expected and Unexpected Symptoms/Toxic Events:

- **Grade 0**
No monitoring necessary.
- **Grade 1 and Grade 2**
Monitor as needed until problem has resolved (i.e., Grade 0), stabilized (i.e., remains as Grade 1 or Grade 2), or is otherwise explained. If Grade 1 or Grade 2 symptoms persist, the physician will assess whether study medication is to be discontinued or whether symptom management should be initiated.
- **Grade 3 and Grade 4 Toxicities:**
If any Grade 3 or Grade 4 toxicity occurs, ascertain cause of event and study relatedness. If symptoms are related to the study drug, the dose of the drug should be reduced by 50% as follows:

Study Drug	50% Dose Reduction	Frequency	If toxicity improves to grade 0, 1, or 2
Eflornithine or matched placebo	250 mg (1 tab)	Daily	Continue dosing at 50%

If Grade 3 or 4 toxicity persists at 50% dose level, the patient can be given a 4 week drug holiday. After the 4 week drug holiday, the patient may be re-challenged at the aforementioned 50% dose reduction level for 4 weeks. Patient will be removed from protocol treatment if there is a cumulative delay of study intervention >90 days.

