10.0 STUDY CALENDAR

Required Studies	Month 0 (Pre-Study)	Study Start	Month 3 (± 14 days)	Month 6 (± 30 days)	Month 9 (± 14 days)	Month 12 (± 14 days)	Month 15 (± 14 days)	Month 18 [10] (± 30 days)	Month 21 (± 14 days)	Month 24 (± 30 days)
PATIENT EVALUATIONS										
Consent & Enrollment [14]	X									
Patient information [1]	X									
History & Physical [13]	X		X	X	X	X	X	X	X	X
Pill Diary [2]		X	X	X	X	X	X	X		X
Toxicity Notation		X	X	X	X	X	X	X	X	X
Laboratory tests [3]	X		X	X	X	X	X	X		X
Pregnancy Test [12]	X									
Audiometry [4]	X							X		
DIAGNOSTIC EVALUATIONS										
Endoscopy [5]	X			X				X		X
Histology assessment	X			X				X		X
H. pylori status [11]	X			X				X		X
INTERVENTIONS										
Dispense study drug [6]		X	X	X	X	X	X			
Adherence assess [7]			X	X	X	X	X	X		
H. pylori treatment [8]				X						(X) [9]

Study Calendar notes:

1. The subject assessment at enrollment includes demographic information and risk factor assessment.
2. While participant is on the protocol intervention, the pill diary is reviewed at each visit.
3. The laboratory tests include CBC (Hgb, Hematocrit, WBC, platelets), liver tests (bilirubin, AST, ALT) and creatinine.
4. Audiometry is performed at the pre-study visit (after all eligibility criteria are met), and at 18 months. Patients are screened for hearing impairment at each study visit, and referred for audiometry, if indicated.
5. Endoscopy with gastric biopsy mapping for histology assessment is the standard of care. The index endoscopy is performed for clinical indications. Samples obtained at the time of the index endoscopy per SOC and prior to patient consent for this study may be submitted for research once informed consent is obtained. The Month 24 endoscopy is considered a surveillance endoscopy in patients with precancerous lesions.[61] The allowable timeframe for each follow-up endoscopy is – 30/+60 days.
6. A three-month supply is dispensed on Day 1 and every 3 months through Month 15. Patients will dose for a total of 18 months and then be followed for an additional 6 months.
7. The adherence assessment consists of the pill count. Phone contact (weekly in months 0-6; monthly in months 6-18) is planned with the patients for adherence assessment, and is performed at the discretion of the study centers.

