11.0 CRITERIA FOR EVALUATION AND ENDPOINT DEFINITIONS

Primary Objective

11.1 The difference in cell DNA damage between patients treated with DFMO and patients treated with placebo at 6 months. The cell DNA damage is measured using the percent positive gastric epithelial cells assessed by IHC for gamma H2AX. The mean difference between the two groups at 6 months will be calculated, accounting for their baseline measurements.

Secondary Objectives

11.2 The difference in cell DNA damage between patients treated with DFMO and patients treated with placebo for 18 months, and then followed for an additional 6 months. The cell DNA damage is measured using the percent positive gastric epithelial cells assessed by IHC for gamma H2AX. The mean difference between the two groups at 18 and 24 months will be calculated, accounting for their baseline measurements. The additional measure of DNA damage, gamma H2AX by IHC and by flow cytometry will also be assessed at 0, 6, 18, and 24 months.

11.3 The differences in the gastritis histopathology score between patients treated with DFMO and patients treated with placebo for a total of 18 months, and followed for an additional 6 months. The gastritis histopathology score is measured with a quantitative scale 0.0-6.0, for atrophy, intestinal metaplasia, and dysplasia. The mean differences between the two groups at 6, 18, and 24 months will be calculated using mixed models, accounting for their baseline measurements.

11.4 Number of patients with quantitative toxicities. Toxicities will be assessed per CTCAE criteria, and each toxicity will be assigned an adverse event (AE) term according to CTCAE definitions (each AE term = unique representation of a specific event used for medical documentation and scientific analyses), and graded as defined by CTCAE (grade 1 = mild; grade 2 = moderate; grade 3 = severe or significant but not immediately life-threatening; grade 4 = life-threatening; grade 5 = death).

10.5 To evaluate whether candidate single nucleotide polymorphisms (SNPs) relevant to eflornithine (DFMO) efficacy.

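### The adverse-event definition leaves out laboratory abnormalities that are asymptomatic and not acted on, and no planned analysis of the scheduled blood panels restores them to the toxicity objective

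*Combined protocol and SAP*

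**What the plan says.** The adverse-event definition in section 15.4.1 reads: "Abnormal laboratory values or diagnostic test results constitute adverse events only if they induce clinical signs or symptoms"; the same sentence then also admits results that need treatment or more diagnostic testing. There are thus three routes by which a laboratory result becomes an event: symptoms, treatment, or further tests.

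The toxicity objective (1.4, repeated as 11.4) is a number of patients: "Toxicities will be assessed per CTCAE criteria, and each toxicity will be assigned an adverse event (AE) term according to CTCAE definitions". Section 9.1 fixes the dictionary: "This study will utilize the CTCAE version 4.0". Section 9.2 then sets the recording rule: "All toxicities are recorded on the Adverse Events Summary Form". None of these three places limits toxicities to those that cause symptoms or lead to action.

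On data collection, note 3 to the study calendar says: "The laboratory tests include CBC (Hgb, Hematocrit, WBC, platelets), liver tests (bilirubin, AST, ALT) and creatinine". The calendar marks these tests at baseline and at Months 3, 6, 9, 12, 15, 18 and 24.

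On analysis, section 12.1 compares AEs and SAEs between the arms as Poisson rates per person-time with exact 95% confidence intervals. It mentions no summary of laboratory values, grades or shifts.

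**The concern.** The definition that decides what counts as an event is narrower than the objective it serves and narrower than the recording rule. An asymptomatic fall in hemoglobin or rise in ALT that nobody treats or works up can be a toxicity to be recorded under 9.2 and a non-event under 15.4.1. The plan does not say which section governs. If 15.4.1 is followed as written, such changes leave the toxicity comparison although they were measured on schedule.

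Two features make this worth settling. First, section 2.0 describes chemoprevention as the long-term use of agents of low or no toxicity in people who are outwardly healthy, so low-grade laboratory effects bear on the safety conclusion. Section 3.1 lists anemia among side effects at 2–3% and carries the warning "Precaution in patients with bone marrow suppression or hematologic disorders". Second, the plan does not say whether a repeat blood draw is a further diagnostic test. A borderline value could then be an event at a site that repeats tests readily and a non-event at a site that does not.

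**Working it through.** The plan gives no figure to reproduce. The check is a comparison of sections, followed by simple arithmetic on what can and cannot be sized.

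**1. The rules side by side**

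| Section | What it governs | Filter on symptoms or action |
|---|---|---|
| 1.4 / 11.4 | Number of patients with CTCAE toxicities | None stated |
| 9.2 | Recording on the AE summary form | None stated |
| 15.4.1 | Whether a laboratory result is an AE | Symptoms, or treatment, or further tests |
| 12.1 | Comparison of arms | AEs and SAEs only |

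The values excluded by 15.4.1 are those with no symptoms and no treatment and no further tests. For Grade 3 or 4, section 9.2 says: "If any Grade 3 or Grade 4 toxicity occurs, ascertain cause of event and study relatedness". For a laboratory value that would usually mean more tests, so the event would be kept. For Grades 1 and 2, 9.2 leaves monitoring to need. The excluded values are therefore most plausibly low grade.

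**2. Does another analysis recover them?** No. Section 12.1 has only the AE and SAE rates. Those are event rates, whereas 1.4/11.4 asks for numbers of patients.

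**3. How much data is involved?** Planned enrolment is 300 (150 per arm).
- All post-baseline panels: 7 × 300 = 2,100 at most.
- Panels through Month 18: 6 × 300 = 1,800 at most.

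The split matters. The section on the purpose of AE reporting (15.3) closes routine reporting 30 days after the last dose, with later events reported only if attributed to the drug, while the calendar marks toxicity notation through Month 24.

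**4. How large is the undercount?** Let p be the true proportion of patients with a given change and c the share that meets 15.4.1. Expected recorded patients per arm = 150 × p × c. The documents do not give c. As an illustration only, take p from the anemia band of 2–3%, which section 3.1 pools over high and low dosing:
- c = 1: 3.0 to 4.5 patients
- c = 0.75: 2.3 to 3.4
- c = 0.50: 1.5 to 2.3
- c = 0.25: 0.8 to 1.1

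**5. Effect on the comparison, if c is equal in both arms**
- Ratio: (p₁ × c) / (p₀ × c) = p₁ / p₀, so it is unchanged in expectation.
- Difference: c × (p₁ − p₀), so it shrinks in proportion to c.
- Precision: for Poisson counts with expectations E₁ and E₀, the standard error of the log rate ratio is approximately √(1/E₁ + 1/E₀). Multiplying both expectations by c multiplies it by 1/√c: 1.15 at c = 0.75, 1.41 at c = 0.50 and 2.00 at c = 0.25.

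**6. Why shift from baseline?** Section 5.2 admits hemoglobin from 11.0 g/dL, AST or ALT up to 2 × IULN and creatinine below 1.6 × IULN. Some patients may therefore start outside normal limits, and worst grade alone would mix baseline status with change on study.

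**The case against.** The sections can be read together. Section 15.4.1 could decide what qualifies as an event, with CTCAE then supplying the term and grade; nothing in 9 or 11.4 says that every out-of-range value is a toxicity. An action-based threshold for laboratory events is a deliberate choice and not in itself a mistake. Patients and sites are blinded (apart from the site pharmacist), and randomization is stratified by site, so uneven test-ordering should not favor an arm. The values are still collected, and the DSMB may see any data it needs. Section 3.1 names no liver or kidney side effect, and its marrow line is a precaution about patients who already have a hematologic problem.

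Most of this stands as a limit on the consequences. It does not remove the point. If the consistent reading is intended, the recording rule in 9.2 and the objective in 11.4 should say so, because as written neither carries the filter. DSMB access is also no substitute for a planned comparison in the final analysis.

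Two stronger readings are not supported. A reader who stops at the first part of the 15.4.1 sentence might infer that every asymptomatic abnormality is dropped; the rest of the sentence keeps those that are treated or investigated. A reader might also infer that 15.4.1 conflicts with the grade-based actions in 9.2. It does not: those actions refer to toxicity without requiring that the AE definition be met, the Grade 3–4 step calls for the cause to be established, and the dose step is itself worded in terms of symptoms. The mismatch lies in recording and counting.

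**Conclusion.** The point holds in this form: followed as written, 15.4.1 removes laboratory changes that are asymptomatic, untreated and not investigated from a toxicity objective that states no such exclusion, and 12.1 has no analysis of the panels that would show them.

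The size is unknown. It depends on the share of abnormalities meeting 15.4.1, which the documents do not give. Under equal capture in the blinded arms the expected rate ratio is unaffected; absolute counts, absolute differences and precision are reduced, and counts may vary with site practice. A reader might infer a specific loss of power, but the documents offer neither rates of laboratory change by arm nor a capture share, so no such figure can be supported. Nor do they suggest bias toward one arm.

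The conclusion rests on the wording of 1.4/11.4, 9.2, 12.1 and 15.4.1 alone. It does not depend on how CTCAE defines individual laboratory grades, which the documents do not reproduce. It is a correction worth making, not a threat to the primary endpoint.

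**What to change.** - **11.4 and 12.1:** state that every scheduled CBC, bilirubin, AST, ALT and creatinine value will be graded by CTCAE v4.0 from the recorded number, whether or not it caused symptoms or action. Report by arm the number of patients by worst post-baseline grade and by shift from baseline, with a risk difference and 95% CI. Show panels through Month 18 separately from Month 24.
- **15.4.1, 9.2 and 11.4:** reconcile them on which laboratory abnormalities enter the toxicity count, and say whether a repeat draw is a further diagnostic test for this purpose. No treatment rule needs to change.

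The cost is a derived variable, one extra table from data already collected, and a clarifying sentence. The downside is that more low-grade laboratory findings will be listed in both arms. Keeping them in their own table, apart from reported AEs, leaves the AE and SAE rates in 12.1 readable as planned.
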